2.3 Relevance

This study will contribute with new knowledge about how patient counselling can be conducted in clinical practise and its effect on the patients' risk of recurrent vascular disease after stroke or TIA. The intervention tested in the study will be implemented in current clinical practise and thereby have a direct effect in the secondary and tertiary prevention of strokes.

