3.2 Objectives

The aim of this study is

- 1) to evaluate the feasibility of a client-centred patient counselling intervention focused on smoking cessation, physical activity, and adherence to preventive medication in patients with minor stroke and transient ischemic attack, and
- 2) to test the effect of that intervention on blood pressure and other cardiovascular risk factors in patients with minor stroke and transient ischemic attack.

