8.1 Sample size calculations

The study in the current form is a randomized feasibility study where the main objective is to test if the intervention and study design is feasible enough for a full size study randomized controlled trial. We will therefore only include 40 participants in this phase of the study.

A full size randomized controlled trial will no doubt require a larger sample size if we were to expect an effect to be found. In a meta-analysis of fairly similar interventional studies Lawrence et al. found that the weighted means of the systolic blood pressure were 132.5 (SD 18.3; n=682) mmHg in the intervention groups and 136.2 (SD 21.5; n=725) in the control groups, respectively, and with a mean difference of 4.21 mmHg (95%CI 2.18-6.24).

Using the estimates from Lawrence et al. we can estimate the sample size needed with the method for comparing two means as reported by Kirkwood & Stern ((12)p 420) with the following assumptions:

- An equal number of participants are allocated to the two groups
- The blood pressure values are approximately normally distributed
- An alpha of 5 percent (probability of Type I error) and a beta of 20 percent (probability of Type II error)

From this it is estimated that we will need a sample-size of 596 (298 in each group), not adjusting for losses to follow-up.

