8.3 Statistical analysis

Hypothesis testing for the secondary outcome (systolic blood pressure) will be done as intention-to-treat (including all participants allocated) using a paired t-test comparing baseline systolic blood pressure with systolic blood pressure measured after 12 weeks. Results will be reported as mean difference of changes with 95 percent confidence intervals.

Tertiary outcome measures will be analyzed as intention-to-treat using unpaired student t-test for continuous variables and either chi-squared test or fisher's exact test for categorical variables. Treatment allocation will be blinded to the investigator.

Statistical analyses will be done in R 3.3.1/R Studio 0.99. A significance level of 5 percent will be considered statistically significant.

9 Validity and bias

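### Blood pressure and eight or nine tertiary outcomes are tested at 5% in 40 patients with no exploratory label, although the plan says an effect needs a larger trial; estimates with confidence intervals should replace the tests

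*Combined protocol and SAP*

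**What the plan says.** - **Objective.** The second aim in section 3.2 is "to test the effect of that intervention on blood pressure and other cardiovascular risk factors".
- **Tests.** Section 8.3 prescribes a hypothesis test of systolic blood pressure. It adds t-tests, chi-squared tests or Fisher's exact tests for the tertiary outcomes. The rule for all of them is "A significance level of 5 percent will be considered statistically significant". The plan gives no multiplicity rule and no exploratory label.
- **Number of outcomes.** The 12-week tertiary table in section 7.1.1 has eight rows: smoking, physical activity, medication adherence, weight, height, waist and hip, fatigue, and self-rated health. Measuring waist and hip separately makes nine.
- **Size.** Section 8.1 makes feasibility the main aim and then says "We will therefore only include 40 participants in this phase of the study". It adds: "A full size randomized controlled trial will no doubt require a larger sample size if we were to expect an effect to be found". It puts that larger trial at 596 patients.
- **Which blood pressure test.** Section 1.3.4 compares the treatment groups with a Student t-test. Section 8.3 names a paired t-test of baseline against 12 weeks, yet reports the result as a mean difference of changes with a 95% confidence interval.
- **Purpose of the results.** Section 1.4 expects estimates of the participation rate and the blood pressure variance, for planning the next trial.

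**The concern.** The plan concedes that 40 patients are too few to expect an effect to be found, and then keeps the machinery of a confirmatory trial. A reader who meets p-values at a declared 5% level, under an objective to test the effect, will take a non-significant result as evidence of no effect and a significant one as proof of benefit. At this size neither inference is sound. The paired wording adds a separate risk: blood pressure may change in both arms between the acute admission and 12 weeks, and a baseline-to-follow-up test would credit such a shared change to the intervention.

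**Working it through.** **Inputs (section 8.1 unless noted).** Difference 4.21 mmHg (95% CI 2.18 to 6.24); "132.5 (SD 18.3; n=682) mmHg in the intervention groups" and SD 21.5 in the control groups; 40 patients. Assumed: 20 per arm, two-sided 5%, no losses.

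**1. The plan's own figure.** n per group = (1.960 + 0.842)² × 2 × 18.3² / 4.21² = 296.6, so 297. The exact t-test version gives 298, or 596 in total, which matches the plan. The match needs the smaller SD in both groups; with both quoted SDs the formula gives 354 per group (708). I therefore show SD 18.3 and the root-mean-square SD, √((18.3² + 21.5²)/2) = 19.96.

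**2. Between-arm test of 12-week values.** SE = SD × √(2/20); the critical value t(0.975; 38 df) is 2.024.

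| | SD 18.3 | SD 19.96 |
|---|---|---|
| SE (mmHg) | 5.79 | 6.31 |
| Smallest significant difference = 95% CI half-width (mmHg) | 11.7 | 12.8 |
| Ratio to 4.21 | 2.8 | 3.0 |
| Noncentrality, 4.21/SE | 0.727 | 0.667 |
| Power (noncentral t) | 10.9% | 10.0% |
| Mean size of significant estimates relative to 4.21 (simulated) | 3.3 | 3.6 |

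Over the cited interval for the effect, power is 6.3-6.6% at 2.18 mmHg and 16-18% at 6.24 mmHg. With an assumed 20% loss (16 per arm) it is 9-10% at 4.21 mmHg.

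**3. Between-arm test of changes.** SD of change = SD × √(2(1 − r)). The documents give no baseline correlation r, so a range is shown.

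| Assumed r | Power, SD 18.3 | Power, SD 19.96 |
|---|---|---|
| 0.3 | 9.2% | 8.5% |
| 0.5 | 10.9% | 10.0% |
| 0.7 | 15.0% | 13.4% |
| 0.8 | 20.2% | 17.7% |

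At r = 0.8 the smallest significant difference in change falls to 7.4 mmHg (SD 18.3) or 8.1 mmHg (SD 19.96).

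**4. The paired test read literally, within one arm.** n = 20, SD 18.3, t(0.975; 19 df) = 2.093, SE = SD of change / √20. For illustration, take a fall of 10 mmHg that is the same in both arms.

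| Assumed r | SE (mmHg) | Chance of p < 0.05 |
|---|---|---|
| 0.5 | 4.09 | 64% |
| 0.7 | 3.17 | 85% |
| 0.8 | 2.59 | 96% |

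The true treatment effect in this example is zero.

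**5. Tertiary outcomes.** The plan gives no effect sizes or SDs for them. For standardised differences of 0.2, 0.5 and 0.8, a t-test with 20 per arm has 9%, 34% and 69% power.

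**The case against.** The strongest defence is that low power is intended and disclosed. Section 8.1 limits the trial to 40 because it is a feasibility study, section 7.1.1 makes blood pressure secondary, and a confidence interval for it is already planned. All of that stands, and the sample size is not the fault. The fault is a 5% test without a label, kept beside that disclosure.

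Several stronger readings are tempting, and the documents do not support them:

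- **That any real effect is missed nine times in ten.** This holds for a between-arm test of 12-week blood pressure at 4.21 mmHg. With change scores the miss rate could be about 80%. For the tertiary outcomes it cannot be computed from the plan; at standardised differences of 0.5 to 0.8 it would be about 66% to 31%. The literal paired test is a different test again.
- **That a p-value decides whether the full trial goes ahead.** No such rule is written. Section 1.4 plans from participation and variance, and section 8.1 takes its effect size from a meta-analysis.
- **That roll-out has already been decided.** Section 2.3 says "The intervention tested in the study will be implemented in current clinical practise", but this may mean only that the trial is delivered within routine care. It is tied to no test result.
- **That there is a 40% chance of a false positive.** 1 − 0.95¹⁰ = 0.40 needs ten independent tests with no true effects. Weight, waist and hip are plainly related, so this is only an upper guide.
- **That one-year events are significance-tested.** Section 8.3 names no test for them.

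It is also fair to say that deleting every test is not the only remedy; labelling p-values exploratory would meet the main point.

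**Conclusion.** The point holds in a limited form. Objective 2 and section 8.3 keep formal 5% tests that section 8.1 says this trial cannot be expected to support. For a between-arm blood pressure comparison at the plan's assumed effect, power is about 10-11% on 12-week values and about 9-20% on changes. A significant difference in 12-week values would have to be roughly three times the assumed effect. These figures rest on equal arms, two-sided testing, no losses, analysis in mmHg and, for changes, an assumed correlation of 0.3-0.8. They say nothing about the tertiary outcomes.

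Sections 1.3.4 and 8.3 also describe different blood pressure tests. The reporting line in 8.3 suggests that a between-arm comparison of changes may be meant, but the named test does not make that comparison. The matter is worth correcting before analysis; it does not undermine the feasibility aim.

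**What to change.** 1. **Section 8.3, blood pressure.** Replace the paired hypothesis test with the between-arm difference and its 95% confidence interval, consistent with section 1.3.4. State in advance whether 12-week values or changes are compared.
2. **Section 8.3, tertiary outcomes.** Report between-arm estimates with 95% confidence intervals, and label any p-values exploratory.
3. **Section 3.2.** Reword objective 2 so that it estimates the effect, to inform the full trial.
4. **Interpretation.** State that no conclusion of effect or of no effect will rest on p-values from this trial.
5. **Section 7.1.1.** Drop height as a 12-week outcome, since counselling cannot change it. The baseline measurement can stay.

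The cost is protocol wording only; no data collection is added. The downside is that no efficacy claim can be made, which the design could not support in any case.

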9.1 Data sources

Administrative information (e.g. time of admission/discharge) is recorded real-time and is therefore reasonably reliable. Medical information (e.g. comorbidities) should be confirmed by clinical or para-clinical tests if possible. All information obtained from the medical records will be verified with the participant to sort out flawed information.

The validity of information obtained from participant interviews can be affected in different ways. There might be problems with the internal validity of the questions used, which means that the

answers that are given might not represent what we think they are. Also participants might not be completely honest in their answers and we do not always have ways to validate them.

The biggest threat to the validity of the study will be missing data; especially due to participants been lost to follow-up. Participants will not always be missing at random. They might have some commonality, which will result in an uneven representation.

9.2 Selection bias

In the study we wish to estimate the feasibility and effect in patients who would receive the treatment in clinical practice. One of the criteria for inclusion in the study is the willingness to participate. Most likely some patients will decline the invitation to participate. There could therefore be a potential selection bias, which could result in a skewed estimation of the effect.

9.3 Confounding variables

In theory the random allocation of treatment should eliminate the effect of other confounders, as they would be equally distributed in the two groups. But given the limited sample-size we cannot be certain that this will be the case. One strategy to avoid this could be to stratify the randomization be a likely confounder (e.g. hypertension or smoking). But at this point we are not sure which confounder would be the best to stratify by and this will therefore be part of the feasibility evaluation.

9.4 Other biases

Ideally both participants and investigators should be blinded as much as possible in clinical trials to avoid confirmation bias. In this study it will not be possible to blind the participants to the treatment group, as they are part of the intervention.

It would be a possibility to blind the assessor who conducts the follow-up measurements. But we cannot be sure that the assessor remains blinded, as the participant might reveal the allocation.

10 Limitations of the study

The study will have several limitations.

Although a randomized controlled trail is optimal for testing treatment effects, this study design also has some disadvantages. Because we select eligible patients to be included in the study we will also introduce a selection bias. To make the study more feasible with a small sample size we will have to exclude patients who are likely not going to complete the intervention or who have needs beyond what we treat in our setting, e.g. patients with addictions. This will of course reduce the generalizability of the study.

This also means that we cannot use data from this study to estimate the prevalence of lifestyle- and behavioural factors in the target population. The prevalence of such factors will be important in estimating how big an effect of the intervention we could expect in the target population. If we wanted to estimate the prevalence we would need a representative sample of the population.

Patients with other types of neurological diseases could potentially benefit from similar lifestyle and behavioural interventions. Part of the purpose of the study is to establish a treatment option for patients with minor stroke and transient ischemic attacks who are discharged to their own home, because treatment options for this patient group is limited at the moment. If we can establish a feasible

and effective treatment for this patient group the next step would be to test the feasibility and effect in other types of patients.

To estimate the effect of a treatment we have to compare it to something else. As there is already an established patient pathway for patients with stroke we can only compare the new treatment to the 'usual care' to see if it is superior to this. The disadvantage of this is that the usual care can vary between hospitals and countries. This can influence the transferability of the results from the study setting to other clinical settings.

11 Ethical considerations

The study will be conducted in accordance with the Helsinki-declaration (13); including respect for the participants' autonomy and right to informed consent. The participants will be informed that the participation in the study as a whole and the single parts of it will be voluntary and that they have the right to decline participation at any time and without giving a cause for their refusal.

The inconveniences of participating will be minor and we are convinced that the potential benefits will outweigh the drawbacks. The main inconveniences of the study will be withdrawing symptoms, associated with smoking cessation, and muscle soreness from increased physical activity. Generally this will be both minor and transient.

The use of a control group as a comparison is necessary if we wish to find evidence of the hypothesised effect of the treatment and gain a better understanding of the variation in the outcome measures. It will also be necessary to test the feasibility of the randomization process prior to the design of a full scale randomized controlled trial. The treatment of the participants in the control group will at no point be inferior to the treatment of non-participants.

11.1 Project approval

The study has been reviewed by the Regional Scientific Ethics Comity (H-17040484). They ruled that this type of intervention did not require an ethics committee approval.

The gathering, storage, and handling of sensitive personal data will require consent from the study participants and an approval from the Danish Data Protection Agency.

11.1.1 Confidentiality and anonymity

All sensitive and identifiable data will be kept confidential in accordance with the guidelines from the Danish Data Protection Agency. Doing the project period the data will be semi-anonymized (personal identifiers, e.g. names and CPR numbers, are kept separate from all other data). When the study is finished the data will be anonymized by deleting all identifiable data.

11.2 Authorship and publication rights

Results of the study will be published in peer-review scientific journals as early as possible. Results will be published regardless of them being positive, negative, or inconclusive.

The principal investigator ([name]) will make the first draft of all publications under the supervision of the other members of the project group. The order of authorship will be in order of contribution and has been agreed upon in the project group beforehand. The rights and responsibilities of the authors will be in accordance with the *The Danish Code of Conduct for Research Integrity* (14).

12 Project management

[figure not shown]
12.1 Project group

The execution of the project will mainly be managed by [name] (RN) under supervision of [name] (MD).

The whole project group will participate in the design of the study and the analysis, evaluation, and interpretation of the study results.

13 Timeline and milestones

If three participants are recruited per week the desired number of participants could be included over a 14 week period. With the follow-up period of 12 weeks it will then take 25 weeks from the first participant is included to the last participant is finished.

13.1 Project organization

The project was initiated as part of the *CIRE neuro/psyk* research program in collaboration between Nordsjællands Hospital, Hillerød; The Metropolitan University College, Copenhagen; and The University Hospitals Centre for Health Research UCSF, Copenhagen University Hospital (Rigshospitalet).

The instigators of the *CIRE neuro/psyk* research program consist of researchers and managers from UCSF and Metropolitan University College, in collaboration with the UCSF steering committee consisting of representatives of the hospital managers in Region Hovedstaden.

